1.5.2 DURVALUMAB DOSE

A population PK model was developed for durvalumab using monotherapy data from a Phase I study (study 1108; N=292; doses= 0.1 to 10 mg/kg Q2W or 15 mg/kg Q3W; solid tumors). Population PK analysis indicated only minor impact of body weight (WT) on the PK of durvalumab (coefficient of ≤ 0.5). The impact of body WT-based (10 mg/kg Q2W) and fixed dosing (750 mg Q2W) of durvalumab was evaluated by comparing predicted steady state PK concentrations (5th, median and 95th percentiles) using the population PK model. A fixed dose of 750 mg was selected to approximate 10 mg/kg (based on median body WT of ~ 75 kg). A total of 1000 patients were simulated using body WT distribution of 40-120 kg. Simulation results demonstrate that body WT-based and fixed dosing regimens yield similar median steady state PK concentrations with slightly less overall between-patient variability with fixed dosing regimen.

Similar findings have been reported by others[55]–[58]. Wang and colleagues investigated 12 monoclonal antibodies and found that fixed and body size-based dosing perform similarly, with fixed dosing being better for 7 of 12 antibodies [56]. In addition, they investigated 18 therapeutic proteins and peptides and showed that fixed dosing performed better for 12 of 18 in terms of reducing the between-patient variability in pharmacokinetic/pharmacodynamics parameters [57].

A fixed dosing approach is preferred by the prescribing community due to ease of use and reduced dosing errors. Given expectation of similar pharmacokinetic exposure and variability, we considered it feasible to switch to fixed dosing regimens. Based on average body WT of 75 kg, a fixed dose of 1500 mg Q4W durvalumab (equivalent to 20 mg/kg Q4W) is included in the combination therapy phases of the current study. Weight based dosing at 20 mg/kg will be utilized for any patient whose body weight drops below 30 kg while on the combination treatment.

For the monotherapy phase, Q3W dosing will be employed with fixed dose of 1120 mg, in order to accommodate the 6 week monotherapy lead-in timing. Patients randomized to durvalumab monotherapy will then transition to the Q4W dosing at initiation of combination phase, as above.

1.6 BENEFIT/RISK AND ETHICAL ASSESSMENT

1.6.1 POTENTIAL BENEFITS

Patients with platinum resistant ovarian cancer have a poor prognosis with typical response rates of 0-20% and median PFS of approximately 3 months and OS ranging between 8 and 17 months across a large number of clinical trials employing cytotoxic and biological antineoplastic therapies[2], [3]. Emerging data from clinical trials investigating immune checkpoint inhibitors targeting PD1 pathways reveal that approximately 10-15% of patients with platinum resistant ovarian cancer respond to checkpoint inhibitor monotherapy[8]. Furthermore, many of the responses are durable in nature lasting many months. However, ongoing trials reveal that combination therapies are required in order to improve this low response rate. The expected synergy with AXL inhibition represents a valuable and important avenue of investigation in this patient population with no better alternative treatment options.

1.6.2 OVERALL RISKS

Monoclonal antibodies directed against immune checkpoint proteins, such as programmed cell death ligand 1 (PD-L1) as well as those directed against programmed cell death-1 (PD-1) or cytotoxic T-lymphocyte antigen-4 (CTLA-4), aim to boost endogenous immune responses directed against tumor cells. By stimulating the immune system however, there is the potential for adverse effects on other tissues.

Most adverse drug reactions seen with the immune checkpoint inhibitor class of agents are thought to be due to the effects of inflammatory cells on specific tissues. These risks are generally events with a potential inflammatory or immune mediated mechanism and may require more frequent monitoring and/or unique interventions such as immunosuppressants and/or endocrine therapy. These immune mediated effects can occur in nearly any organ system, and are most commonly seen as gastrointestinal AEs such as colitis and diarrhea, pneumonitis/interstitial lung disease (ILD), hepatic AEs such as hepatitis and liver enzyme elevations, skin events such as rash and dermatitis and endocrinopathies including hypo- and hyper-thyroidism.

1.6.2.1 AVB-S6-500

AVB-S6-500 has been well tolerated across all doses trialed in initial healthy volunteer single ascending dose and repeat dose trial. There were no serious adverse events. There were no treatment-related changes noted in physical examinations or vital signs. None of the AEs based on laboratory values were deemed clinically significant, none required treatment, and all were asymptomatic. As per protocol, all laboratory values that met CTCAE v 4.03 criteria for subjects given active drug were considered possibly related. None were considered probably/likely or certainly related. Further information can be found in the Investigator's Brochure.

However, the combination of AXL inhibition with durvalumab may result in exacerbation of immune-related adverse effects. Therefore, the risks with the combination include, but are not limited to, the categories as listed within **Section 1.6.2.2**.

1.6.2.2 DURVALUMAB

Risks with durvalumab include, but are not limited to, diarrhea/colitis and intestinal perforation, pneumonitis/ILD, endocrinopathies (hypo- and hyper-thyroidism, type I diabetes mellitus, hypophysitis and adrenal insufficiency) hepatitis/increases in transaminases, nephritis/increases in creatinine, pancreatitis/increases in amylase and lipase, rash/pruritus/dermatitis, myocarditis, myositis/polymyositis, other rare or less frequent inflammatory events including neurotoxicities, infusion-related reactions, hypersensitivity reactions and infections/serious infections.

For information on all identified and potential risks with durvalumab please always refer to the current version of the durvalumab IB.

In monotherapy clinical studies AEs (all grades) reported very commonly ($\geq 15\%$ of patients) are fatigue, nausea, decreased appetite, dyspnea, cough, constipation, diarrhea, vomiting, back pain, pyrexia, asthenia, anemia, arthralgia, peripheral edema, headache, rash, and pruritus. Approximately 9.4% of patients experienced an AE that resulted in permanent discontinuation of durvalumab and approximately 6.5% of patients experienced an SAE that was considered to be related to durvalumab by the study investigator.

The majority of treatment-related AEs were manageable with dose delays, symptomatic treatment, and in the case of events suspected to have an immune basis, the use of established treatment guidelines for immune-mediated adverse events (**Section 6.3.1**).

1.6.3 OVERALL BENEFIT-RISK

Ovarian cancer is the deadliest gynecologic malignancy, with a short progression free interval and limited treatment options at time of recurrence. While checkpoint inhibition has showed exciting initial activity, the rates of response remain low. Therefore, further investigation of novel combinations where synergy is expected, such as with AXL inhibition, represents an essential approach to advancing the care of these women. Additionally, rapid expansion of the use of immunotherapies have demonstrated that the majority of immune-related adverse events are manageable and acceptable in such a patient group with few alternatives. Thus, overall, the risks-benefit ratio is in favor of further investigations to refine checkpoint and AXL inhibitor therapy combinations and their associated toxicities in this population.

2. STUDY OBJECTIVES

2.1 PRIMARY

To determine toxicity profile of the combination of AVB-S6-500 and durvalumab therapy

2.2 SECONDARY

1. To estimate objective response rate to combination AVB-S6-500 and durvalumab therapy
2. To estimate the median immune-related progression free survival (irPFS) as well as overall survival OS by RECIST 1.1 after treatment with combination durvalumab and AVB-S6-500
3. To investigate molecular and immunological changes associated with the combination of AVB-S6-500 and durvalumab; specifically to describe changes in T cell populations (including but not limited to CD3, CD8, CD4, FOXP3) and cell proliferation, as well as report changes in the proportion of macrophage phenotypes M1 and M2 (with phenotypic markers potentially including arginase1, CD11b, PDL-1, and CD206)

2.3 EXPLORATORY

1. To evaluate blood and tissue-based biomarkers for immune related adverse events and disease progression
2. To investigate impact and possible sensitization of pretreatment with AVB-S6-500 monotherapy on subsequent combination of durvalumab and AVB-S6-500
3. To evaluate for molecular and immunologic differences between pre-treatment with single agent AVB-S6-500 as compared to durvalumab

3. ORIGINAL STUDY DESIGN

This is a randomized phase I/II trial of the combination of immune checkpoint inhibitor therapy and AXL inhibition in patients with recurrent platinum resistant EOC. The design is based on the clinical rationale that the combination of durvalumab and AVB-S6-500 may have increased efficacy but at the risk of potentially greater toxicity. This trial will determine appropriate combination dosing and then, based on efficacy and safety assessments, allow for development of a superior suitable regimen for a follow-up phase III investigation based on these efficacy and toxicity tradeoffs. It will also be informative regarding response rates associated with this combination regimen and will generate key preliminary data to determine impact on irPFS and if pretreatment with either durvalumab or AVB-S6-500 impacts subsequent response to the combination of both therapies. Furthermore, translational correlative studies will include immune profiling and ribonucleic acid (RNA) expression analysis of tumor at enrollment, following monotherapy, and on combination treatment to investigate biological correlates for response, possible sensitization of immune microenvironment, and any indication of adverse event. Progression during investigational agent treatment cycles will be defined based on immune-related response criteria (irRC; including computed tomography (CT) confirmation at least 5 weeks apart to determine progression).

3.1 END OF STUDY ENROLLMENT

In the first quarter of 2021, study supporters Aravive and AstraZeneca made the decision to end enrollment based on available data after the 5th evaluable subject completed treatment on the safety lead-in.

[figure not shown]

Figure 2. Study Schema

Dosing schedule as above demonstrates investigational product at week of administration, where A = AVB-S6-500 monotherapy, D= durvalumab monotherapy, and A+D = AVB-S6-500 + durvalumab combination therapy

* Patients receiving the recommended Phase 2 dose (RP2D) will then be included in the primary analysis of the combination therapy. However, these patients will continue on the Safety Lead-in dosing schedule and will not participate in the Phase 2 monotherapy. See de-escalation dosing regimens below.

† Sample size calculations account for predicted 8% dropout rate due to toxicity.

‡ Dosing schedule shown reflects the starting dose for the dose escalation. This may be adjusted for the de-escalation schedule below and determination of the RP2D.

Table 1. Dosing for Dose Escalation

Dose Level	Durvalumab + AVB-S6-500
Dose Level 0 (Initial dose)	durvalumab (1500mg Q4W), AVB-S6-500 (10mg/kg Q2W)
Dose level 1	durvalumab (1500mg Q4W), AVB-S6-500 (15mg/kg Q2W)
Dose level 2	durvalumab (1500mg Q4W), AVB-S6-500 (20mg/kg Q2W)

3.2 SAFETY LEAD-IN

The trial will begin with a dose escalation phase to determine the recommended Phase 2 dose (RP2D). The design for dose escalation is provided in **Section 9**. The dose level established in the dose escalation phase will define the recommended dosing for subsequent combination treatment. Those patients treated at the RP2D will continue on treatment and will contribute to primary analysis of combination therapy.

Of note, prior to receipt of any treatment, all patients will undergo a computed tomography (CT) scan to determine baseline volume of disease. An initial pre-treatment biopsy and blood samples will be obtained to measure immune function in both the pretreated tumor environment and systemically.

To investigate translational aims, all patients participating in safety lead-in cohorts will undergo a biopsy and blood sampling after receiving 6 weeks of treatment.

Refer to the Schedule of Assessments in **Table 6** for complete details (**Section 6.5**).

3.3 PHASE II

The Phase II portion of the study will begin after the RP2D is established in the Safety Lead-in. In Phase II, eligible subjects first will participate in a 6-week monotherapy cycle (Cycle 0) with either AVB-S6-50 (ARM I) or durvalumab (ARM II) before proceeding to receive the combination therapy at the RP2D. We will randomize 3:1 to AVB-S6-500 and durvalumab monotherapy arms, respectively. Subjects randomized to Arm 1 will receive single agent AVB-S6-500 (Q2W), and subjects randomized to Arm 2 will receive durvalumab (fixed Q3W dosing) during the monotherapy cycle. The monotherapy dose for each agent will be based on the combination RP2D established in the Safety Lead-in. Prior to receiving monotherapy treatment, all subjects will undergo a CT scan to determine initial volume of disease. An initial pre-treatment biopsy and blood samples will be obtained to measure immune function in both the pretreated tumor environment and systemically.

Following 6 weeks of monotherapy treatment, a repeat CT scan will be performed and an additional biopsy will be obtained. Of note, this CT scan serves as the new baseline imaging from which response to combination will be compared.

All patients who have completed monotherapy treatment without limiting toxicity will then be treated with combination therapy at the RP2D. Patients will receive treatment until progression or unacceptable toxicity with combination therapy. An additional biopsy will be obtained after 2 cycles of therapy, and CT scans will be performed every 8 weeks.

Refer to the Schedules of Assessments in **Table 7** and **Table 8** for complete details (**Section 6.5**).

4. PATIENT SELECTION

4.1 INCLUSION CRITERIA

Inclusion criteria will be assessed within 28 days of starting study treatment:

1. Ability to provide signed informed consent.
2. Age \geq 18 years at time of study entry.
3. Patient is willing and able to comply with the protocol for the duration of the study including undergoing treatment and scheduled visits and examinations including follow up.
4. Histology (reviewed at MDACC) showing recurrent high grade epithelial ovarian, peritoneal, or fallopian tube cancer.
5. Platinum resistant or refractory disease as defined by progression of disease on a platinum-containing regimen or recurrence of disease within 180 days of previous platinum treatment.
6. Have measurable disease based on modified RECIST 1.1. For the purposes of this study measurable disease is defined at least one "target lesion" that can be accurately measured in at least one dimension (longest dimension to be recorded). Each target lesion must be >20 mm when measured by conventional techniques, including palpation, plain x-ray, computed tomography (CT), and magnetic resonance imaging (MRI), or >10 mm when measured by spiral CT. The

- target lesion must be distinct from other tumor areas selected for pre-treatment biopsies. Pre-treatment imaging must be performed within 4 weeks of starting therapy.
7. Eastern Cooperative Oncology Group (ECOG) performance status of 0 or 1.
 8. Life expectancy of ≥ 12 weeks.
 9. Body weight >30 kg. Note: if subject's weight falls below 30 kg during study but the patient is otherwise eligible to continue investigational therapy the dose of durvalumab will be modified to be weight-based (20 mg/kg for the 1500 mg dose; modification is not required for 1120 mg dose). Refer to **Section 5.1.2** and **Appendix C** for complete details.
 10. Adequate normal organ and marrow function as defined below.
 - a. Hemoglobin ≥ 9.0 g/dL.
 - b. Absolute neutrophil count (ANC) $> 1500/\text{mm}^3$.
 - c. Platelet count $\geq 100 \times 10^9/\text{L}$ ($> 75,000/\text{mm}^3$).
 - d. Serum bilirubin $\leq 1.5 \times \text{ULN}$. This will not apply to patients with confirmed Gilbert's syndrome (persistent or recurrent hyperbilirubinemia that is predominantly unconjugated in the absence of hemolysis or hepatic pathology), who will be allowed only in consultation with their physician.
 - e. AST (SGOT)/ALT (SGPT) $\leq 2.5 \times \text{ULN}$ unless liver metastases are present, in which case it must be $\leq 5 \times \text{ULN}$.
 - f. Measured creatinine clearance (CL) $>40 \text{ mL/min}$ or Calculated creatinine CL $>40 \text{ mL/min}$ by the Cockcroft-Gault formula (Cockcroft and Gault 1976) or by 24-hour urine collection for determination of creatinine clearance:

$$\text{Creatinine CL} = \frac{\text{Weight (kg)} \times (140 - \text{Age})}{72 \times \text{serum creatinine (mg/dL)}} \times 0.85$$

11. Evidence of post-menopausal status or negative serum pregnancy test for female pre-menopausal patients. Women will be considered post-menopausal if they have been amenorrheic for 12 months without an alternative medical cause. The following age-specific requirements apply:
 - a. Women <50 years of age would be considered post-menopausal if they have been amenorrheic for 12 months or more following cessation of exogenous hormonal treatments and if they have luteinizing hormone and follicle-stimulating hormone levels in the post-menopausal range for the institution or underwent surgical sterilization (bilateral oophorectomy or hysterectomy).
 - b. Women ≥ 50 years of age would be considered post-menopausal if they have been amenorrheic for 12 months or more following cessation of all exogenous hormonal treatments, had radiation-induced menopause with last menses >1 year ago, had chemotherapy-induced menopause with last menses >1 year ago, or underwent surgical sterilization (bilateral oophorectomy, bilateral salpingectomy or hysterectomy).
12. Patients must have no currently available standard of care treatment options

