7.1.4.1 MEASURABLE LESIONS

Measurable lesions must be accurately measured in at least one dimension (longest diameter in the plane of measurement is to be recorded) with a minimum size of:

- 10 mm by CT scan (irrespective of scanner type) and MRI (no less than double the slice thickness and a minimum of 10 mm).
- 10 mm caliper measurement by clinical exam (when superficial).

Malignant lymph nodes are considered pathologically enlarged and measurable, a lymph node must be \geq 15 mm in short axis when assessed by CT scan (CT scan slice thickness recommended to be no greater than 5 mm).

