7.1.4.2 NONMEASURABLE LESIONS

Nonmeasurable lesions are defined as all other lesions (or sites of disease), including small lesions (longest diameter < 10 mm or pathological lymph nodes with ≥ 10 to < 15 mm short axis). Lesions considered truly nonmeasurable include the following: leptomeningeal disease, ascites, pleural/pericardial effusion, lymphangitic involvement of skin or lung, abdominal masses/abdominal or organomegaly identified by physical exam that is not measurable by reproducible imaging techniques.

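### Inclusion 6 sets lesion size limits that conflict with Section 7.1.4, so its explicit limits could admit a patient who has no Section 7 target lesion but still counts in the ORR

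*Combined protocol and SAP*

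**What the plan says.** **Entry.** Item 6 of Section 4.1 first names the response standard and then gives a study-specific rule. It begins: "Have measurable disease based on modified RECIST 1.1. For the purposes of this study measurable disease is defined at least one 'target lesion". The rule works on a single dimension, the longest, and no short axis appears in it. For spiral CT the limit is "or >10 mm when measured by spiral CT"; for conventional techniques, among which it lists palpation, CT and MRI, the lesion has to exceed 20 mm. Nodes are not mentioned. The target lesion must also be separate from the areas chosen for pre-treatment biopsy.

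**Response assessment.** Section 7.1.4.1 sets the minimum at "10 mm by CT scan (irrespective of scanner type) and MRI", or "10 mm caliper measurement by clinical exam (when superficial". A node must reach "15 mm in short axis when assessed by CT scan". Section 7.1.4.2 treats everything else as nonmeasurable, and its examples of small lesions include nodes whose short axis lies between 10 and just under 15 mm.

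**Scoring and counting.** Section 7.2.1 defines partial response only through the sum of target-lesion diameters. Section 7.2.2 gives non-target disease no partial-response category. Section 9.1.2 puts everyone with at least one combination dose in the Efficacy Analysis Set, with no condition on measurable disease. ORR is the first secondary objective (Section 2.2) and is estimated with a 90% confidence interval (Section 9.2).

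**The concern.** The lesion that qualifies a patient for entry should be one on which response can later be scored. Here the two definitions differ in the dimension measured, in the dependence on scanner type, and in the treatment of nodes. A small node can meet the entry limits and then be classed as nonmeasurable. If the patient has nothing else to follow, she contributes to the ORR denominator but cannot contribute a partial response. In a cohort of about five, how one such patient is classified matters to the reading of the ORR.

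**Working it through.** The plan gives no figure for this point, so there is nothing to reproduce. The check compares the rules, applies them to an example node, and bounds the effect.

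**1. The rules side by side**

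| Lesion | Inclusion 6 | Section 7.1.4 |
|---|---|---|
| Non-nodal, spiral CT | >10 mm longest dimension | 10 mm minimum |
| Non-nodal, other CT or MRI | >20 mm | 10 mm minimum |
| Superficial, clinical exam | >20 mm (palpation) | 10 mm (caliper) |
| Lymph node | no separate rule | at least 15 mm short axis |

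**2. An example node**, 14 mm long axis by 11 mm short axis on spiral CT (dimensions chosen for illustration):

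- Inclusion 6 size limit: 14 > 10, met.
- Section 7.1.4.1: 11 < 15, not measurable.
- Section 7.1.4.2: 10 ≤ 11 < 15, nonmeasurable.

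**3. Route to response.** Every partial-response row in Table 10 needs a complete or partial response in target lesions. No row covers a patient without target lesions. If such nodes are all she has outside the biopsy site, partial response is closed to her. A non-target complete response (nodes under 10 mm and a normal tumor marker, Section 7.2.2) remains defined, but Table 10 does not say what overall response it yields.

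**4. If the node were recorded as a target anyway.** By short axis, a 30% fall gives 0.7 × 11 = 7.7 mm. This is already below the 10 mm nodal threshold for complete response in Section 7.2.1. For a single node, a partial response needs 0.7 × baseline ≥ 10 mm, so baseline ≥ 10/0.7 = 14.29 mm. Below that the partial-response category is empty, although a complete response could be scored. By longest diameter, a fall from 14 to 0.7 × 14 = 9.8 mm could be scored as a 30% decrease. Either recording would contradict Section 7.1.4.2.

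**5. Size for one such patient.** The maximum attainable partial-response rate falls from 1 to (n − 1)/n, a loss of 1/n:

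- n = 5 (fifth evaluable subject, Section 3.1): 1/5 = 20 points.
- n = 15 (maximum in step 3 of the dose-finding rule, Section 9): 1/15 = 6.7 points. The opening of Section 9 gives 18 instead; 1/18 = 5.6 points.

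These are ceilings, reached only if she would otherwise certainly have had a partial response. As an assumption, take her chance of response to be the 10% to 30% used in the Section 9 design. The expected loss is then p/n:

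- n = 5: 0.10/5 to 0.30/5 = 2 to 6 points.
- n = 15: 0.10/15 to 0.30/15 = 0.7 to 2 points.

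**The case against.** The best defense is that Inclusion 6 opens by requiring disease measurable under modified RECIST 1.1, which is the title of Section 7.1. A screener who applies both sentences would import the 15 mm nodal rule and turn the patient away. This stands in part: a reader should not infer that she is plainly eligible. But the next sentence gives a study-specific definition with different numbers and no nodal rule. The MRI and non-spiral CT limits conflict with Section 7 on any reading.

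The biopsy condition also narrows the case. Pre-treatment biopsy is planned (Sections 3.2 and 6.6.2), and the target lesion must be separate from it. A patient with a single node and no other disease would generally not qualify; a second disease site is needed. The problem arises only when all disease outside the biopsy site is nonmeasurable under Section 7. Any other Section 7 target lesion restores the route to partial response.

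A reader might go further and infer that the ORR is biased downward. The documents do not support that. They give no count of such patients, non-target complete response stays defined, and Section 7.1.4.3 does not repeat a size limit when targets are chosen. A site might therefore record the node, although Section 7.1 says that efficacy endpoints are derived programmatically from RECIST 1.1.

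Nor does the opposite mismatch harm the ORR. Non-nodal lesions between 10 and 20 mm by MRI or non-spiral CT are measurable in Section 7 but do not qualify at entry. That affects eligibility only, and a stricter entry limit can be a legitimate choice.

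**Conclusion.** The two definitions conflict and should be reconciled. Under its explicit size limits, Inclusion 6 could admit a patient with no Section 7 target lesion and no route to partial response, who would nevertheless count in the ORR.

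The weight is modest. One such patient costs at most 20 points of attainable partial-response rate at n = 5, or 6.7 points at n = 15, and less in expectation. The conclusion assumes that the screener applies the stated size limits without importing the nodal rule, that all her non-biopsied disease is nodes of 10 to under 15 mm short axis, and that she receives a combination dose. Whether anyone fits this description cannot be told from the documents. ORR is secondary to toxicity, and Section 9 states that the retained Phase II text no longer applies.

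**What to change.** Replace the size limits in Inclusion 6 with a requirement for at least one measurable lesion as defined in Section 7.1.4.1, keeping the condition that it be distinct from the biopsy site.

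Since Section 3.1 reports that enrollment was ended, rewording the entry criterion may change little by itself. Two further steps deal with the patients already treated:

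- Check each treated patient's baseline lesions against Section 7.1.4.1.
- Report ORR in all treated patients and, alongside it, in those with at least one Section 7 target lesion.

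The cost is one edited sentence and one small extra tabulation. Eligibility would shift slightly, in either direction, only if any patient were still to be enrolled.
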